14.1 Populations for Analyses

• Safety Analysis Dataset: Safety analyses will be conducted for all evaluable participants who took at least one dose of study intervention.

• **Primary Efficacy Dataset**: participants who receive at least olaparib for 14 days of 21-day course and one dose of pembrolizumab are considered to be evaluable for efficacy evaluation.

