13.2 Criteria for Study Endpoint Evaluability

- All patients who receive at least one dose of olaparib and pembrolizumab are considered to be evaluable for toxicity.
- All patients who receive at least olaparib for 14 days of 21-day course and one dose of pembrolizumab are considered to be evaluable for efficacy evaluation.

- Patients who enroll with a complete response on platinum-based treatment are evaluable and a radiographical disease recurrence by RECIST v 1.1 will be considered a progression.
- Patients who are screened eligible but subsequently withdraw from the study prior to receiving pembrolizumab with olaparib are considered inevaluable and will be replaced on the study.

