A two stage design will be employed only in Cohort A with co-primary endpoints ORR by iRECIST and 6-month PFS rate⁷ by RECIST v1.1. An initial cohort of 20 patients will be treated. If 14 or more patients are alive and progression free at the 6 months follow-up or if 6 or more objective responses are observed, an additional 13 patients will be accrued for a total of 33 patients. If 23 or more of the 33 patients are alive and progression free at 6 months from start of treatment or if 12 or more objective responses are observed, we can conclude that the regimen is sufficiently active to warrant further testing in this group of patients. We will also evaluate the progression-free survival from the consent date secondarily to the treatment start date (C1D1). We used the reference from historical data for these co-primary endpoints. 6-months PFS rate was 50% and ORR was 20% in singleagent olaparib study arm compared to placebo control arm in maintenance setting⁷. This design yields 81% power to detect a true 6-month PFS rate of 77% or more and it yields 81% power to detect a true ORR of at least 43%. It yields approximately 0.95 probability of a negative result if the true 6-month PFS rate is no more than 53% and the true ORR is no more than 20%. The type I error for the ORR endpoint is 0.02 and the type I error for the PFS endpoint is 0.028 and so the overall type I error of the composite design is bounded at 0.05 (the sum of the two type I error rates for PFS and RR) while the type II error rate for the composite design is 0.09 (each design has a type II error rate of 0.09). The probability of early termination was calculated as the product of the probability of early termination for the PFS endpoint (0.904) and the probability of early termination for the RR endpoint (0.804), resulting in a probability of early termination of 0.73 for the composite endpoint. These calculations assume that ORR and PFS are independent, , the type 1 error slightly decreases if ORR and PFS are positively correlated, which is very likely. The calculations also assume that the 6 month PFS endpoint is binary. Patients who are lost to follow up before their 6 months PFS

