evaluation and who did not respond or do not have documented response before their being lost to follow up will be counted as events (nonresponders/progressors) for the composite primary endpoint. However this will be uncommon. If after the first stage we meet the rule of observing 6 or more responses out of the 20 patients enrolled in the first stage, then no waiting is required and we can proceed with enrollment to the second stage. However, if we do not observe 6 out of 20 responses after the first stage, we will halt accrual after the first 20 patients until we obtain the 6-month PFS status for these 20 patients. The interim look for Cohort A will not affect accrual to Cohorts B and C.

Cohorts B and C will be exploratory and will enroll 15 patients each. ORR will be estimated using the binomial distribution along with exact 95% confidence intervals. With 15 accrued patients, we can estimate the DCR to within +/- 25% margins of error with 95% confidence.

Secondary objectives

Adverse events will be summarized descriptively and tabulated separately for each cohort. DCR will be estimated using binomial proportions along with exact 95% confidence intervals while PFS and OS will be estimated using the Kaplan-Meier method separately for each of the 3 cohorts. CEA and CA 19-9 will be summarized using medians and interquartile range.

Exploratory objectives

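### The primary efficacy set omits treated Cohort A patients with under 14 days of olaparib and the scoring of lost responders is left open, so observed rates can be biased upward and the error rate can rise

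*Protocol*

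**What the plan says.** Two sections define who counts for efficacy. Section 14.1 (Primary Efficacy Dataset): "participants who receive at least olaparib for 14 days of 21-day course and one dose of pembrolizumab are considered to be evaluable". Section 13.2 gives the same condition: "All patients who receive at least olaparib for 14 days of 21-day course and one dose of pembrolizumab are considered to be evaluable". Section 13.2 replaces only patients who withdraw before receiving the combination. It provides no replacement for a treated patient who fails the 14-day condition.

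Section 14.0 sets the Cohort A rule in fixed counts of patients. Stage 1: "An initial cohort of 20 patients will be treated". The trial continues as follows: "If 14 or more patients are alive and progression free at the 6 months follow-up or if 6 or more objective responses are observed". The final PFS criterion is: "If 23 or more of the 33 patients are alive and progression free at 6 months from start of treatment". The alternative route to success is 12 or more responses. The error rates are calculated "if the true 6-month PFS rate is no more than 53% and the true ORR is no more than 20"%.

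On loss to follow-up before the 6-month PFS evaluation, section 14.0 says that patients "who did not respond or do not have documented response before their being lost to follow up will be counted as events" for the composite primary endpoint, and that this will be uncommon. It does not say how a patient lost after a documented response is scored for 6-month PFS.

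Section 13.1.9 starts PFS at the initiation of study treatment and counts death as an event.

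**The concern.** Membership of the efficacy set depends on what happens after treatment begins. A patient who starts both drugs and dies on day 10 is a PFS event under section 13.1.9, yet is not in the set used for the primary analysis. In a single-arm trial judged against a fixed external rate, leaving out early failures favours the regimen.

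The two sections also do not fit together. Section 14.0 speaks of 20 patients treated and 23 of 33, whereas section 14.1 admits only evaluable patients. If some treated patients are not evaluable, either fewer than 33 remain and the denominator is unclear, or enrolment continues until 33 are evaluable. These readings have different error rates.

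The loss rule uses one sentence for two endpoints. Not penalising a documented responder is right for ORR. It does not settle 6-month PFS, because a responder lost at month 3 was never seen at 6 months. At stake is which patients enter the go/no-go count for the only cohort with a powered analysis.

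**Working it through.** **Inputs from section 14.0.** Stage 1: 20 patients, continue with at least 14 progression free or at least 6 responses. Final: 33 patients, success with at least 23 progression free or at least 12 responses. Null rates are 53% (PFS) and 20% (ORR); alternatives are 77% and 43%.

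**Assumed.** The share *d* of treated patients with under 14 days of olaparib is not in the protocol; 3%, 5% and 10% are used. One patient in 33 is 1/33 = 3%.

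**Step 1: reproduce the plan.** With b the binomial probability,

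P(success) = Σ over x ≥ 14 of b(20, x, p) × P(Bin(13, p) ≥ 23 − x),

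and likewise with 6 and 12 for ORR. The composite rule (continue if either is met, succeed if either is met) is enumerated under independence, as the protocol assumes.

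| Quantity | Stated | Recomputed |
|---|---|---|
| PFS alpha at 53% | 0.028 | 0.0281 |
| ORR alpha at 20% | 0.02 | 0.0201 |
| Composite alpha | bound 0.05 | 0.0496 |
| PFS power at 77% | 81% | 0.806 |
| ORR power at 43% | 81% | 0.809 |

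The stated error rates hold when all 33 treated patients are counted. The composite has almost no slack below 0.05.

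**Step 2: exclusion without refilling, cut-offs fixed.** Removing a failure leaves the number of successes unchanged, so the chance of reaching 14 and then 23 is unchanged. PFS alpha stays at 0.0281, and by the same argument ORR alpha stays at 0.0201. Only the reported proportion moves, because its denominator shrinks.

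**Step 3: exclusion with refilling to 20 and 33 evaluable patients, all excluded patients being failures.** The rate in the set becomes p/(1 − d).

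| d | PFS rate: 0.53/(1 − d) | ORR: 0.20/(1 − d) | PFS alpha | Composite alpha |
|---|---|---|---|---|
| 0 | 53.0% | 20.0% | 0.028 | 0.050 |
| 3% | 54.6% | 20.6% | 0.042 | 0.069 |
| 5% | 55.8% | 21.1% | 0.055 | 0.087 |
| 10% | 58.9% | 22.2% | 0.104 | 0.151 |

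The rate columns also give the expected observed rate in the evaluable set without refilling.

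**Step 4: not all excluded patients are failures.** Suppose half are. With refilling the PFS rate is (0.53 − d/2)/(1 − d): at d = 5%, 0.505/0.95 = 53.2% and alpha is 0.029; at d = 10%, 0.48/0.90 = 53.3% and alpha is 0.031. Without refilling, lost successes lower the count: alpha is 0.014 at 5% and 0.007 at 10%.

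**Step 5: lost responders scored as progression free.** Let *s* be the share of all patients who are lost responders and would otherwise have been PFS failures. The counted rate is 0.53 + s. For s = 1%, 2%, 3% and 5%, PFS alpha is 0.036, 0.046, 0.057 and 0.088. At an ORR of 20%, s = 1% means that 0.01/0.20 = 5% of responders are affected. The protocol does not prescribe this scoring; the figures show what it would cost.

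**The case against.** The strongest reply is that the written rule does not inflate the error rate. It uses fixed counts, speaks of patients treated, and replaces only those who withdraw before receiving the combination. On that reading step 2 applies and PFS alpha stays at 0.028. This stands, and it makes every figure in step 3 conditional on refilling.

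The other replies have force too:
- Sections 10.1 and 15.0 let a patient who stops one drug for toxicity remain on study. A patient with little olaparib can therefore be progression free at 6 months, and step 4 shows that the effect can then nearly vanish or reverse.
- Radiographic progression within two weeks should be rarely recorded: the first scheduled on-treatment scan is at week 9, and Cohort A patients enter with at least 4 months of stable or responding disease. Early deaths and toxicity stops remain possible.
- Section 14.0 cites a historical PFS rate of 50%, below the 53% null. At a true 50%, PFS alpha is 0.0125, and 0.026 with 5% excluded and refilled, still under 0.028. The composite is then 0.056, slightly above 0.05.

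Three stronger readings are tempting but unsupported. A reader might infer that the error rate necessarily rises; step 2 shows otherwise. A reader might infer that the benchmark trial applied no such filter because it timed PFS from randomization; that gives its time origin, not its analysis population. A reader might take the loss rule to score lost responders as PFS successes; the text is silent on them.

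None of this removes the conflict between sections 14.0 and 14.1, or the bias in the reported rates when early stoppers are mainly failures.

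**Conclusion.** The point holds as a matter of population and scoring. The primary efficacy set is selected on exposure after treatment start and can discard PFS events that section 13.1.9 counts. It is not reconciled with the 20 and 33 in section 14.0. Where early stoppers are mainly failures, the observed rates are biased upward: if all are failures, a true 53% reads as 54.6% to 58.9% for shares of 3% to 10%.

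The effect on type I error is conditional. It is nil without refilling and with cut-offs of 14 and 23. It reaches PFS alpha 0.042 to 0.104 and composite alpha 0.069 to 0.151 only with refilling, with every excluded patient a failure, and with shares of 3% to 10% that the protocol does not supply. Scoring lost responders as progression free would raise the error separately.

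This should be fixed, because it decides who counts in the go/no-go rule. It does not show that the stated error rates are wrong.

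**What to change.** Amend sections 13.2, 14.0 and 14.1 to state that:

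1. The 20 and the 33 are all Cohort A patients who receive any study drug.
2. Early stoppers without a response count as non-responders, and as not progression free unless their 6-month status is documented.
3. Any patient lost before the 6-month assessment counts as a PFS failure, whether or not a response was recorded. A documented response stands for ORR.
4. The 14-day evaluable set is kept as a sensitivity analysis.

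With these statements the design figures apply as written: PFS alpha 0.028, ORR alpha 0.02, composite within 0.05. The cost is wording in three sections and observed rates that may be slightly lower. No new data are needed, and the sample size and cut-offs do not change.

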15.0 TOXICITIES/RISKS/SIDE EFFECTS

The investigators will assess each participant to evaluate for potential new or worsening AEs as specified in the Trial Flow Chart and more frequently if clinically indicated. Adverse experiences will be graded and recorded throughout the study and during the follow-up period according to NCI CTCAE Version 5 (see Appendix 2). Toxicities will be characterized in terms regarding seriousness, causality, toxicity grading, and action taken with regard to trial treatment.

An adverse event is defined as any untoward medical occurrence in a patient or clinical investigation participant administered a pharmaceutical product and which does not necessarily have to have a causal relationship with this treatment. An adverse event can therefore be any unfavorable and unintended sign (including an abnormal laboratory finding, for example), symptom, or disease temporally associated with the use of a medicinal product or protocol-specified procedure, whether or not considered related to the medicinal product or protocol-specified procedure. Any worsening (i.e., any clinically significant adverse change in frequency and/or intensity) of a preexisting condition that is temporally associated with the use of the Merck's product, is also an adverse event.

Changes resulting from normal growth and development that do not vary significantly in frequency or severity from expected levels are not to be considered adverse events. Examples of this may include, but are not limited to, teething, typical crying in infants and children and onset of menses or menopause occurring at a physiologically appropriate time.

Adverse events may occur during the course of the use of POLAR (Merck product of pembrolizumab and olaparib) in clinical trials, or as prescribed in clinical practice, from overdose (whether accidental or intentional), from abuse and from withdrawal.

All AEs, SAEs and other reportable safety events that occur after the consent form is signed but before treatment allocation/randomization must be reported by the investigator if the participant is receiving placebo run-in or other run-in treatment, if the event cause the participant to be excluded from the study, or is the result of a protocol-specified intervention, including but not limited to washout or discontinuation of usual therapy, diet, or a procedure.

If a patient requires discontinuation of either olaparib or pembrolizumab for reasons of toxicity and if in the opinion of the treating MD the patient is continuing to derive benefit, the patient is able to continue on study.

- All AEs from the time of treatment allocation/randomization through 30 days following cessation of study treatment must be reported by the investigator.
- All AEs meeting serious criteria, from the time of treatment allocation/randomization through 90
 days following cessation of study treatment, or 30 days following cessation of study treatment if the
 participant initiates new anticancer therapy, whichever is earlier must be reported by the investigator.
- All pregnancies and exposure during breastfeeding, from the time of treatment allocation/randomization through 120 days following cessation of study treatment, or 30 days

following cessation of study treatment if the participant initiates new anticancer therapy must be reported by the investigator.

 Additionally, any SAE brought to the attention of an investigator at any time outside of the time period specified above must be reported immediately by the investigator if the event is considered to be drug-related.

Investigators are not obligated to actively seek AE or SAE or other reportable safety events in former study participants. However, if the investigator learns of any SAE, including a death, at any time after a participant has been discharged from the study, and he/she considers the event to be reasonably related to the study treatment or study participation, the investigator must promptly notify Merck.

Possible Side Effects of pembrolizumab

COMMON, SOME MAY BE SERIOUS

In 100 people receiving pembrolizumab more than 20 and up to 100 may have:

- Itching of the skin
- Loose or watery stools
- Cough

OCCASIONAL, SOME MAY BE SERIOUS

In 100 people receiving pembrolizumab from 4 to 20 may have:

- Joint pain
- Rash
- Fever
- Back pain
- Pain in the belly
- Loss of skin color
- Not enough thyroid hormone (hypothyroidism), which may make you feel tired, gain weight, feel cold, or have infrequent or hard stools
- Low levels of salt in the blood (hyponatremia), which may make you feel tired, feel confused, have a headache, have muscle cramps, and/or feel sick to your stomach
- Inflammation of the lungs (pneumonitis), which may make you feel short of breath and cough
- Too much thyroid hormone (hyperthyroidism), which may make you feel anxious, feel angry, have trouble sleeping, feel weak, tremble, sweat, feel tired, or have loose and watery stools
- Infusion-related reaction (IRR; like an allergic reaction), which may make you feel dizzy or faint, feel flushed, get a rash, have a fever, feel short of breath, experience a decrease in your blood pressure, or have pain at the infusion site, either while you are receiving the infusion or just after
- Inflammation of the bowels/gut (colitis), which may cause severe pain in your belly, with loose or watery stools, and black, tarry, sticky stools, or stools with blood or mucus

 Severe inflammation of the skin (Stevens-Johnson syndrome and/or toxic epidermal necrolysis), which may cause peeling of the skin, itchiness, and/or skin redness. The skin inflammation could be widespread throughout your body. More severe skin reactions may involve the inside of your mouth, the surface of your eyes and genital areas, and/or may cause the top layer of skin to peel from all over your body, which can cause a severe infection.

RARE, AND SERIOUS

In 100 people receiving pembrolizumab 3 or fewer may have:

- Inflammation of the nerves (Guillain-Barré syndrome), which may cause pain, weakness or tingling in your hands and feet, and may spread to your legs, arms, and upper body, leading to severe muscle weakness and possible temporary paralysis
- Inflammation of the muscles (myositis), which may make you feel weak or have pain in your muscles
- Inflammation of the pancreas (a gland in your abdomen that controls sugar levels; pancreatitis), which may cause severe pain in the top part of your belly, and the pain may move to your back; you may feel sick to your stomach, and experience vomiting that gets worse when you eat
- Inflammation of the eye (uveitis), which may cause eye redness, blurred vision, sensitivity to light, eye pain, headaches, or seeing "floaters"
- Inflammation of the liver (hepatitis), which may make you feel sick to your stomach and vomit, feel like not eating, feel tired, have a mild fever, have a pain in the right side of your belly, yellow eyes and skin, and dark urine
- Inflammation of the pituitary gland (a gland in the head; hypophysitis), which
 may make you feel sick to your stomach or have headaches, changes in your
 behavior, double vision, few to no menstrual cycles, weakness, vomiting, and
 dizziness or fainting
- Adrenal glands (glands on top of the kidneys) may not make enough hormone (adrenal insufficiency), which could cause tiredness; weight loss; muscle weakness; feeling faint; having joint, muscle, and belly aches; nausea; vomiting; and loose or watery stools; fever; salt craving; and sometimes darkening of the skin like a suntan
- Type 1 diabetes, a condition that can result in too much sugar in your blood, making you feel thirstier than usual, with frequent urination, and weight loss. You are likely to need regular insulin shots to treat this condition.
- Inflammation of the kidney (nephritis), which may make you pass less urine or have cloudy or bloody urine, swelling, and low back pain
- Inflammation of the middle layer of your heart wall (myocarditis), which may make it difficult for your heart to pump blood through your body, causing chest pain, shortness of breath, and swelling of the legs. You may experience a fast or irregular heartbeat that may cause dizziness or fainting.
- Inflammation of the thyroid gland, which may lead to changes in your heart rate, blood pressure, body temperature, and the rate at which food is converted into energy (thyroiditis)
- Myasthenic syndrome/myasthenia gravis including exacerbation, conditions that
 may make you feel weak and tired, and may cause drooping eyelids, blurred or
 double vision, difficulty swallowing, slurred speech, weakness in your arms and
 legs, or difficulty breathing

- Sarcoidosis, the formation of small clusters of immune cells (granulomas) in parts of your body, such as your lymph nodes, eyes, skin, or lungs
- Inflammation of the brain (encephalitis), with confusion and fever. Symptoms may include disorientation, memory problems, seizures (fits), changes in personality and behavior, difficulty speaking, weakness or loss of movement in some parts of your body, and loss of consciousness
- Inflammation of the spinal cord (myelitis), which may cause pain, numbness, tingling, or weakness in the arms or legs, bladder or bowel problems including needing to urinate more frequently, urinary incontinence, difficulty urinating, and constipation

Possible Side Effects of olaparib

COMMON, SOME MAY BE SERIOUS

In 100 people receiving olaparib more than 20 and up to 100 may have:

- Feeling sick to your stomach (nausea)
- Vomiting
- Tiredness/weakness (fatigue)
- Indigestion/heartburn (dyspepsia)
- Loss of appetite
- Headache
- Changes in the way food tastes (dysgeusia)
- Dizziness
- Loose or watery stools (diarrhea): Call the study doctor right away if you have continuous or severe diarrhea
- Cough
- Shortness of breath (dyspnea)
- Decrease in the number of red blood cells (anemia), which can be associated with shortness of breath, fatigue, pale skin, or fast heartbeat, and may require a transfusion for treatment
- Decrease in the total number of white blood cells (leukopenia) and in white blood cells called neutrophils (neutropenia) that protect you from infection, which can be associated with fever

OCCASIONAL, SOME MAY BE SERIOUS

In 100 people receiving olaparib from 4 to 20 may have:

- Sore mouth (stomatitis)
- Skin rash
- Increase in the level of creatinine in the blood. This test result can suggest a
 potential problem with your kidneys. Symptoms of kidney damage include
 decreased urine output, swelling of your legs, ankles, and feet from retaining
 fluids, unexplained shortness of breath, fatigue, nausea, confusion, and chest
 pain.
- Pain in the stomach area under the ribs (upper abdominal pain)

RARE, AND SERIOUS

In 100 people receiving olaparib 3 or fewer may have:

- Allergic reactions; symptoms include tingling or itching in the mouth, hives, swelling of the lips, face tongue, throat, and other parts of the body, wheezing, nasal congestion, trouble breathing, abdominal pain, diarrhea, nausea, or vomiting
- Itchy rash or swollen, reddened skin (dermatitis)
- Increase in the size of red blood cells (not associated with any symptoms); this condition is treatable but, in rare cases, a blood transfusion may be required

